8.10.1.7. Maternal Participants: 6-Month-Postdelivery Visit (168 to 210 Days After Delivery)

- Collect a blood sample of approximately 25 mL for serologic assessments. Refer to the SRM for blood sample collection guidelines.
- Record details of any antenatal steroid treatment, monoclonal antibodies, blood transfusions (eg, whole blood, packed cells), or Rho(D) immune globulin (eg, RhoGam) given since the last visit.
- Record details of any nonstudy vaccinations given since the last visit.
- Record any medication as described in [Section 6.5.3](#).
- Ask the maternal participant to contact the site staff or investigator if a medically attended event (eg, doctor's visit, emergency room visit) or hospitalization occurs.
- Ask the maternal participant to contact the site staff or investigator if her infant meets the acute illness visit criteria.
- Record AEs as described in [Section 8.3](#) and [Section 10.3.3](#).
- Complete the maternal participant's source documents.
- The investigator or an authorized designee completes the CRF.

8.10.1.8. Maternal Participants: 12-Month-Postdelivery Follow-up (350-378 Days After Delivery)

- Record details of any antenatal steroid treatment, monoclonal antibodies, blood transfusions (eg, whole blood, packed cells), or Rho(D) immune globulin (eg, RhoGam) given since the last visit.
- Record details of any nonstudy vaccinations given since the last visit.
- Record any medication as described in [Section 6.5.3](#).

- Record AEs as described in [Section 8.3](#) and [Section 10.3.3](#).
- Complete the maternal participant's source documents.
- The investigator or an authorized designee completes the CRF.

8.10.1.9. Maternal Participants: Unscheduled Reactogenicity Visits

If the maternal participant reports 1 or more of the following, a contact **must** occur as soon as possible between the maternal participant and the investigator, or a medically qualified member of the study site staff, to assess if an unscheduled visit is required.

- redness at the injection site measuring >20 measuring device units (>10.0 cm),
- swelling at the injection site measuring >20 measuring device units (>10.0 cm),
- severe injection site pain,
- fever $\geq 102.1^{\circ}\text{F}$ ($\geq 39.0^{\circ}\text{C}$),
- severe fatigue,
- severe headache,
- severe nausea,
- severe vomiting,
- severe diarrhea,
- severe muscle pain,
- severe joint pain.
- any necrosis at the injection site,
- any exfoliative dermatitis.

A site visit should be scheduled as soon as possible to assess the extent of the reaction unless:

- The maternal participant is unable to attend the unscheduled visit, or
- The reaction is no longer present at the time of the contact, or
- The maternal participant recorded an incorrect value in the e-diary (confirmation of an e-diary data entry error), or

- The investigator determines that the visit is not required.

This contact will be recorded in the maternal participant's source notes and in the CRFs.

If the maternal participant is unable to attend the unscheduled visit, any ongoing reactions must be assessed at the next scheduled visit.

The reactogenicity events should be assessed by the investigator or a medically qualified member of the site staff such as a study physician or a study nurse, as applicable to the investigator's local practice, who will:

- Measure oral temperature.
- Measure the maternal participant's heart rate.
- Measure the maternal participant's blood pressure (seated).
- Measure the minimum and maximum diameters of redness (if present).
- Measure the minimum and maximum diameters of swelling (if present).
- Assess any necrosis at the injection site.
- Assess any exfoliative dermatitis.
- Assess any injection site pain that is present in accordance with the reactogenicity grading scale provided in [Section 8.2.2](#).
- Assess for lymphadenopathy associated with any local reaction.
- Assess any systemic events (fatigue, headache, nausea, vomiting, diarrhea, muscle pain, or joint pain) that are present in accordance with the reactogenicity grading scale provided in [Section 8.2.3](#).
- Ask the maternal participant if she attended an emergency room visit or was hospitalized.
- For severe pain at the injection site associated with an emergency room visit or hospitalization, severe systemic events associated with an emergency room visit or hospitalization, or any necrosis or exfoliative dermatitis, the investigator must assess these events in accordance with the Assessment of Intensity grading scale provided in [Section 10.3.3](#) for documentation on the AE CRF.
- Record any medication as described in [Section 6.5.3](#).
- Record AEs as described in [Section 8.3](#) and [Section 10.3.3](#).

- Complete the source documents.
- The investigator or an authorized designee will complete the CRFs.

Maternal participants will be instructed to contact the site to report any significant illness, medically attended event, or hospitalization that occurs during the study period. Study staff may contact the participant to obtain additional information on Grade 3 events entered into the e-diary.

8.10.2. Infant

8.10.2.1. Infant Participants: Visit 1 – Birth (Birth to 7 Days After Birth)

- Assign a single infant participant identifier using the IRT system (or equivalent).
- Ensure a cord blood sample of up to approximately 10 mL was collected. Cord blood is collected from the umbilical cord vein attached to the placenta prior to the blood clotting within the cord after the umbilical cord has been clamped and cut. This sample should be labeled with the **infant's participant ID number**.
- If cord blood is unavailable, a venous blood sample may be collected in the infant participants up to 24 hours after birth. The volume of blood collected will be based on the weight of the infant (refer to [Table 5](#)).
- Ensure and document that all of the infant inclusion criteria and none of the infant exclusion criteria are met.
- Collect demography (including complete date of birth [ie, dd-Mmm-YYYY], sex, race, and ethnicity). The date of birth will be collected to critically evaluate the immune response and safety profile by age.
- Obtain and record the infant's length, head circumference, and weight at birth.
- Obtain and record the infant's birth data, including gestational age, Apgar score, and Ballard score.
- Obtain and record background factors as described in [Section 10.5](#).
- Measure vital signs, including rectal temperature, heart rate, oxygen saturation by pulse oximetry, and respiratory rate.
- Perform physical examination, if not performed as part of routine care, evaluating any clinically significant abnormalities within the following body systems: general appearance; skin; head, eyes, ears, nose, and throat; heart; lungs; abdomen; back; musculoskeletal; extremities; genitourinary; neurological; and lymph nodes. Abnormal results must be recorded on source documents as well as the physical examination and AE pages of the CRF.

- Record details of any congenital abnormality.
- Record nonstudy vaccine information.
- Record monoclonal antibodies (eg, Synagis) or blood transfusions (eg, whole blood, packed cells) given since birth.
- Record any medication as described in [Section 6.5.5](#).
- Record AEs as described in [Section 8.3](#) and [Section 10.3.3](#).
- Ask the parent(s)/legal guardian(s) to contact the investigator immediately if any significant illness or hospitalization occurs or if the infant meets the acute illness visit criteria.
- Complete the infant participant's source documents.
- The investigator or an authorized designee completes the CRF.

8.10.2.2. Infant Participants: Visit 2 – 1-Month Follow-up (28 to 35 Days After Birth)

- Measure vital signs, including rectal temperature, heart rate, and respiratory rate.
- Obtain and record infant's length, head circumference, and weight.
- Obtain and record background factors as described in [Section 10.5](#).
- Perform physical examination, if not performed as part of routine care, evaluating any clinically significant abnormalities within the following body systems: general appearance; skin; head, eyes, ears, nose, and throat; heart; lungs; abdomen; back; musculoskeletal; extremities; genitourinary; neurological; and lymph nodes. Newly identified abnormal findings must be recorded on source documents and the physical examination page and, if considered clinically significant in the judgment of the investigator/examiner, on the AE page of the CRF.
 - Obtain and record details of any newly emergent congenital medical history.
- Obtain and record details of any vaccinations, monoclonal antibodies (eg, Synagis), or blood transfusions (eg, whole blood, packed cells) given since the last visit.
- For infants randomly assigned to the Visit 2 (1-month follow-up) and Visit 4 (4-month follow-up) sampling schedule, collect a blood sample of up to 5.0 mL for serologic assessments based on the infant's weight (refer to [Table 5](#)).
- Record any medication as described in [Section 6.5.5](#). Record AEs as described in [Section 8.3](#) and [Section 10.3.3](#).

- Ask the parent(s)/legal guardian(s) to contact the investigator immediately if any significant illness or hospitalization occurs or if the infant meets the acute illness visit criteria.
- Complete the infant participant's source documents.
- The investigator or an authorized designee completes the CRF.

8.10.2.3. Infant Participants: Visit 3 – 2-Month Follow-up (49 to 63 Days After Birth)

- Measure vital signs, including rectal temperature, heart rate, and respiratory rate.
- Obtain and record the infant's length, head circumference, and weight.
- Obtain and record background factors as described in [Section 10.5](#).
- Perform physical examination, if not performed as part of routine care, evaluating any clinically significant abnormalities within the following body systems: general appearance; skin; head, eyes, ears, nose, and throat; heart; lungs; abdomen; back; musculoskeletal; extremities; genitourinary; neurological; and lymph nodes. Newly identified abnormal findings must be recorded on source documents and the physical examination page and, if considered clinically significant in the judgment of the investigator/examiner, on the AE page of the CRF.
 - Obtain and record details of any newly emergent congenital medical history.
- Obtain and record details of any vaccinations, monoclonal antibodies (eg, Synagis), or blood transfusions (eg, whole blood, packed cells) given since the last visit.
- For infants randomly assigned to the Visit 3 (2-month follow-up) and Visit 5 (6-month follow-up) sampling schedule, collect a blood sample of up to 5.0 mL for serologic assessments based on the infant's weight (refer to [Table 5](#)).
- Record any medication as described in [Section 6.5.5](#).
- Record AEs as described in [Section 8.3](#) and [Section 10.3.3](#).
- Ask the parent(s)/legal guardian(s) to contact the investigator immediately if any significant illness or hospitalization occurs or if the infant meets the acute illness visit criteria.
- Complete the infant participant's source documents.
- The investigator or an authorized designee completes the CRF.

8.10.2.4. Infant Participants: Visit 4 – 4-Month Follow-up (112 to 126 Days After Birth)

- Measure vital signs, including rectal temperature, heart rate, and respiratory rate.
- Obtain and record the infant’s length, head circumference, and weight.
- Obtain and record background factors as described in [Section 10.5](#).
- Perform physical examination, if not performed as part of routine care, evaluating any clinically significant abnormalities within the following body systems: general appearance; skin; head, eyes, ears, nose, and throat; heart; lungs; abdomen; back; musculoskeletal; extremities; genitourinary; neurological; and lymph nodes. Newly identified abnormal findings must be recorded on source documents and the physical examination page and, if considered clinically significant in the judgment of the investigator/examiner, on the AE page of the CRF.
 - Obtain and record details of any newly emergent congenital medical history.
- Obtain and record details of any vaccinations, monoclonal antibodies (eg, Synagis), or blood transfusions (eg, whole blood, packed cells) given since the last visit.
- For infants randomly assigned to the Visit 2 (1-month follow-up) and Visit 4 (4-month follow-up) sampling schedule, collect a blood sample of up to 5.0 mL for serologic assessments based on the infant’s weight (refer to [Table 5](#)).
- Record any medication as described in [Section 6.5.5](#).
- Record AEs as described in [Section 8.3](#) and [Section 10.3.3](#).
- Ask the parent(s)/legal guardian(s) to contact the investigator immediately if any significant illness or hospitalization occurs or if the infant meets the acute illness visit criteria.
- Complete the infant participant’s source documents.
- The investigator or an authorized designee completes the CRF.

8.10.2.5. Infant Participants: Visit 5 – 6-Month Follow-up (168 to 210 Days After Birth)

- Measure vital signs, including rectal temperature, heart rate, and respiratory rate.
- Obtain and record the infant’s length, head circumference, and weight.
- Obtain and record background factors as described in [Section 10.5](#).
- Perform physical examination, if not performed as part of routine care, evaluating any clinically significant abnormalities within the following body systems: general

appearance; skin; head, eyes, ears, nose, and throat; heart; lungs; abdomen; back; musculoskeletal; extremities; genitourinary; neurological; and lymph nodes. Newly identified abnormal findings must be recorded on source documents and the physical examination page and, if considered clinically significant in the judgment of the investigator/examiner, on the AE page of the CRF.

- Obtain and record details of any newly emergent congenital medical history.
- Obtain and record details of any vaccinations, monoclonal antibodies (eg, Synagis), or blood transfusions (eg, whole blood, packed cells) given since the last visit.
- For infants randomly assigned to the Visit 3 (2-month follow-up) and Visit 5 (6-month follow-up) sampling schedule, collect a blood sample of up to 5.0 mL for serologic assessments based on the infant's weight (refer to Table 5).
- Record any medication as described in [Section 6.5.5](#).
- Record AEs as described in [Section 8.3](#) and [Section 10.3.3](#).
- Ask the parent(s)/legal guardian(s) to contact the investigator immediately if any significant illness or hospitalization occurs or if the infant meets the acute illness visit criteria.
- Complete the infant participant's source documents.
- The investigator or an authorized designee completes the CRF.

8.10.2.6. Infant Participants: Visit 6 – 12-Month Follow-up (350 to 378 Days After Birth)

- Measure vital signs, including rectal temperature, heart rate, and respiratory rate.
- Obtain and record the infant's length, head circumference, and weight.
- Obtain and record background factors as described in [Section 10.5](#).
- Perform physical examination, if not performed as part of routine care, evaluating any clinically significant abnormalities within the following body systems: general appearance; skin; head, eyes, ears, nose, and throat; heart; lungs; back; abdomen; musculoskeletal; extremities; genitourinary; neurological; and lymph nodes. Newly identified abnormal findings must be recorded on source documents and the physical examination page and, if considered clinically significant in the judgment of the investigator/examiner, on the AE page of the CRF.
 - Obtain and record details of any newly emergent congenital medical history.

- Obtain and record details of any vaccinations, monoclonal antibodies (eg, Synagis), or blood transfusions (eg, whole blood, packed cells) given since the last visit.
- Record any medication as described in [Section 6.5.5](#).
- Record AEs as described in [Section 8.3](#) and [Section 10.3.3](#).
- Complete the infant participant's source documents.
- The investigator or an authorized designee completes the CRF.

CCI

CCI

CCI

C
C
|

CCI

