1.3.2. Schedule of Activities for Infant Participants

Visit Number	1	2	3	4	5	6
Visit Description	Birth	1-Month Follow-up	2-Month Follow-up	4-Month Follow-up	6-Month Follow-up	12-Month Follow-up
Visit Window (Days)	Birth to 7 Days After Birth	28 to 35 Days After Birth	49 to 63 Days After Birth	112 to 126 Days After Birth	168 to 210 Days After Birth	350 to 378 Days After Birth
Assign infant participant identifier	X					
Demography	X					
Collect background factors	X	X	X	X	X	X
Collect birth outcome information (including Ballard score)	X					
Vital signs ^a	X	X	X	X	X	X
Physical examination	X	X	X	X	X	X
Length, head circumference, and weight ^{b,c}	X	X	X	X	X	X
Record nonstudy vaccine information	X	X	X	X	X	X
Record monoclonal antibodies (eg, Synagis) or blood transfusions (eg, whole blood, packed cells)	X	X	X	X	X	X
Review eligibility	X					
Cord blood sample ^c (~10 mL) for serologic assessment	X					
Blood draw for serologic assessment (up to 5 mL per blood sample based on weight) ^b		X	X	X	X	
Record concomitant medication taken to treat an AE	X	X	X	X	X	X
Record adverse events, medically attended adverse events, serious adverse events, and adverse events of special interest, as appropriate ^d	X	X	X	X	X	X

Visit Number	1	2	3	4	5	6
Visit Description	Birth	1-Month Follow-up	2-Month Follow-up	4-Month Follow-up	6-Month Follow-up	12-Month Follow-up
Visit Window (Days)	Birth to 7 Days After Birth	28 to 35 Days After Birth	49 to 63 Days After Birth	112 to 126 Days After Birth	168 to 210 Days After Birth	350 to 378 Days After Birth
Surveillance reminder contact	After delivery, contact the infant participants' parents approximately every week until approximately 6 months after delivery					

- a. Vital signs include rectal temperature, heart rate, oxygen saturation by pulse oximetry (**Visit 1 only**), and respiratory rate.
- b. Infant participants will be randomly assigned to 1 of 2 blood sampling schedules. Blood samples will be collected either at Visit 2 (1-month follow-up) and Visit 4 (4-month follow-up) **OR** at Visit 3 (2-month follow-up) and Visit 5 (6-month follow-up). Weight will be used to determine the volume of blood that can be collected.

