3.2. Infant Participant

Primary Objective Infant Participant	Estimands	Primary Endpoints Infant Participant
To assess the safety of maternal immunization in infants born to women ≥ 18 through 49 years of age who were vaccinated with 1 dose of RSV vaccine during pregnancy	In infant participants born to the maternal participants receiving 1 dose of investigational product: 
• The percentage of infant participants with specific birth outcomes• The percentage of infant participants having AEs• The percentage of infant participants having SAEs, AEs of special interest (congenital anomalies, developmental delay), and MAEs	
• Specific birth outcomes• AEs from birth to 1 month of age• SAEs, AEs of special interest (congenital anomalies, developmental delay), and MAEs through 12 months of age• Congenital anomalies (defined as structural or functional anomalies [eg, metabolic disorders] that occur during intrauterine life and can be identified prenatally, at birth or later in life²⁶)

Secondary Objective Infant Participant	Estimands	Secondary Endpoints Infant Participant

To describe RSV antibody levels in infants born to women ≥ 18 through ≤ 49 years of age who were vaccinated with 1 dose of RSV vaccine during pregnancy
	
In infant participants born to maternal participants receiving 1 dose of investigational product and in compliance with the key protocol criteria (evaluable participants):
 
 • Functional antibody levels estimated by the GMT for RSV A– and RSV–B neutralizing antibody titers • GMR, estimated by the ratio of the GMTs for RSV A– and RSV–B neutralizing antibody titers of the RSV vaccine group and the placebo group 	
 • RSV A– and RSV B–neutralizing antibody titers measured at: 
 • birth • 1 month • 2 months • 4 months • 6 months 
Note: Infant participants will be randomly assigned to 1 of 2 blood sampling schedules.

CCI

CCI

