10.3.1.1. Definition of MAE

An MAE is defined as a nonserious AE that results in an evaluation at a medical facility.

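### Parents are not asked to report infant medically attended events, and the visible schedule has no contact between the 6- and 12-month visits, so nonserious MAEs in that interval are at risk of under-capture

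*Protocol*

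**What the plan says.** **Endpoint.** Protocol section 3.2 lists among the primary infant endpoints "SAEs, AEs of special interest (congenital anomalies, developmental delay), and MAEs through 12 months of age". Section 10.3.1.1 gives the definition: "An MAE is defined as a nonserious AE that results in an evaluation at a medical facility". Inpatient admission is a seriousness criterion in section 10.3.2, so a hospitalized event is generally an SAE and not an MAE. The typical MAE is a nonserious visit to a doctor or emergency room.

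**What parents are asked.** Sections 8.10.2.1 to 8.10.2.5 (infant Visits 1 to 5) carry the same instruction, to "contact the investigator immediately if any significant illness or hospitalization occurs or if the infant meets the acute illness visit criteria". It has three triggers, and a medically attended event is not one of them.

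**What mothers are asked.** From vaccination to the 6-month postdelivery visit, the mother is told to "contact the site staff or investigator if a medically attended event" or hospitalization occurs. Section 8.10.1.9 tells mothers to "report any significant illness, medically attended event, or hospitalization that occurs during the study period". In the maternal sections for delivery and for 1 and 6 months postdelivery, the separate bullet about the infant asks for contact only (in the 6-month wording) "if her infant meets the acute illness visit criteria".

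**What sites do.** The infant schedule in section 1.3.2 marks the recording of MAEs at all six visits. Section 8.3.1 has infant MAEs reported from Visit 2 to the last visit. Parents are contacted "approximately every week until approximately 6 months after delivery". Visit 5 falls on days 168 to 210 and Visit 6 on days 350 to 378.

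**The concern.** The standing prompt to parents does not match the endpoint that it feeds. Section 8.10.1.9 lists significant illness, a medically attended event and hospitalization as three separate items, so the protocol itself does not treat the first as covering the second. A parent who follows the infant instruction to the letter need not call about a nonserious doctor's visit for something that seems minor, unless it meets the acute illness criteria.

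Until about 6 months, weekly contact and closely spaced visits limit what can be lost. After that, the visible text leaves Visit 6 to recover what happened since Visit 5. Visit 6 (section 8.10.2.6) refers to section 8.3 for recording AEs, and section 8.3.2 prefers open-ended, nonleading questions. Nothing visible prompts a specific question about a doctor's visit several months earlier.

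After Visit 2, only AEs of special interest, MAEs and SAEs are reported for infants. Apart from AEs of special interest, MAEs are then the only category through which nonserious infant events enter the data. SAP section 6.1.2.3 summarizes them through 12 months without a split at 6 months, so weaker late capture would not show in the planned table.

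**Working it through.** **1. Length of the interval.** Inputs: visit windows in Protocol section 1.3.2.

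- Shortest: 350 − 210 = 140 days, which is 140/350 = 40% of follow-up to Visit 6.
- Longest: 378 − 168 = 210 days, which is 210/378 = 56%.
- The longest earlier interval is Visit 4 to Visit 5, at most 210 − 112 = 98 days, and weekly contact covers most or all of it.

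Weekly contact may run slightly past an early Visit 5. If 6 months is taken as 183 days (my assumption), the longest stretch with no scheduled contact is 378 − 183 = 195 days. The shortest stays at 140.

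**2. The plan's own figure.** Protocol Table 6 gives the probability of seeing at least one AE as 1 − (1 − p)^N. For p = 1% and N = 100: 1 − 0.99^100 = 0.634, which matches the stated 63%. All 21 cells of the table reproduce.

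**3. Common MAEs (rates assumed).** Let a be the proportion with an MAE before the gap, fully captured; b the proportion with one in the gap, independent of a; and s the share of infants with a gap MAE for whom it is captured. The reported 12-month proportion is 1 − (1 − a)(1 − b·s), and the loss is (1 − a)·b·(1 − s).

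| a, b | s = 1 | s = 0.9 | s = 0.7 | s = 0.5 |
|---|---|---|---|---|
| 30%, 30% | 51.0% | 48.9% | 44.7% | 40.5% |
| 50%, 30% | 65.0% | 63.5% | 60.5% | 57.5% |
| 50%, 50% | 75.0% | 72.5% | 67.5% | 62.5% |

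Worked cell: 1 − 0.5 × (1 − 0.3 × 0.7) = 1 − 0.5 × 0.79 = 0.605. Over this grid the loss runs from 1.5 to 12.5 percentage points.

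**4. A rare event confined to the gap.** Replace p by s·p in the Table 6 formula, with p = 1%. Pregnancies are singleton, so infants per group are taken as equal to mothers per group: 100 as in Table 6, or 650/5 = 130 at full enrollment.

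| N | s = 1 | s = 0.9 | s = 0.7 | s = 0.5 |
|---|---|---|---|---|
| 100 | 0.634 | 0.595 | 0.505 | 0.394 |
| 130 | 0.729 | 0.691 | 0.599 | 0.479 |

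None of a, b and s comes from the documents. Steps 3 and 4 show how a loss would act, not that one of this size will occur.

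**The case against.** The best reply is that the parent sentence is an urgent call-in prompt and not the collection method. Collection is specified elsewhere. MAEs are marked for recording at all six visits. Section 8.3.1 requires them to the last visit. Section 6.5.5 requires medication taken for MAEs to be recorded up to the final visit, so sites have to ask about MAEs at Visit 6. Section 10.1.7 also requires medical records to be available. This stands, and it defeats the stronger reading that the endpoint **is** under-ascertained. What remains is narrower. The visible procedures document an MAE once someone reports it, but none requires a search for visits that nobody mentions.

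Second, a reader might infer that parents are told to report only significant illness or hospitalization. They are not, because the acute illness visit criteria are a third trigger. Those criteria are redacted, so how many nonserious visits they cover cannot be judged. Redaction also surrounds the infant schedule and interrupts section 8.3.1. Further contacts could be there, so the gap can be stated only for the visible text.

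Third, a reader might infer that a vaccine-placebo difference in infant MAEs will be diluted. No such difference is planned. SAP section 6.1.2.3 gives MAEs as n, % and 95% CI by group and specifies differences only for AEs of special interest. SAP section 3.5.1 limits Tier 2 events to those within 30 days. All analyses are descriptive.

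Finally, a pointed question at Visit 6 may seem to conflict with the preference for open-ended questioning. That is a preference, and asking whether the infant was seen at a medical facility suggests no symptom and is the same in every arm.

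**Conclusion.** The concern holds as a risk of under-capture of nonserious infant MAEs, mainly in the 140 to 210 days between Visits 5 and 6. The mismatch in wording and the visible interval are facts of the text. That MAEs will actually be missed is an inference, and its size is unknown.

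If MAEs are missed, the effect should be a lower reported percentage in each group and not a bias toward one arm. Section 6.3.1 blinds the mother, the investigator and site staff other than dispensers and administrators, and section 6.3.3 keeps investigators blinded throughout. This assumes that capture depends on the family and site and not on the vaccine received. The documents do not support a claim of certain bias or of a diluted treatment comparison.

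Hospitalizations are less exposed, because parents are explicitly asked to report them. The point is a low-cost improvement to the ascertainment of a primary endpoint. It does not challenge the design, the sample size or the planned analysis.

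**What to change.** 1. In Protocol sections 8.10.2.1 to 8.10.2.5, add any medically attended event to the existing parent instruction, with a doctor's visit and an emergency room visit as examples, as the maternal sections do. Keep the three present triggers. Visit 5 matters most, because its instruction has to last until Visit 6.
2. In section 8.10.2.6, add a bullet asking whether the infant has been evaluated at a medical facility since Visit 5, with any qualifying event recorded as an MAE.

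This changes one sentence in five sections and adds one bullet at Visit 6. It adds no visit and changes no treatment, sample size or analysis. The cost is more calls from parents for sites to handle, and infant MAE percentages that may be slightly higher.
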